#### 3. Schedule of Assessments:

Visit	Domain	Assessment
BL	Characterize Participants	Baseline Questionnaire (including TBI screen) MOCA
BL	Beliefs about Compensation	Disability Application Appraisal Inventory Disability Beliefs Scale
BL	Substance Use	SCID substance abuse module
BL, 4, 12	Substance Use	Substance Use Calendar
BL, 12	Alcohol Use	Ethyl Glucoronide
BL	PTSD	Life Events Checklist and Military Sexual Trauma Screen
4	Process	Veterans' understanding of the study assessments and their relationship or lack thereof to the C&P exam
BL, 4, 12	PTSD	CAPS
BL, 4, 12	Other Psych	Beck Depression Inventory II
BL, 4, 12	Service Use	Service Use Calendar
BL, 4, 12	Process	Stage of Change
BL, 4, 12	Other Psych	Response to Stressful Experiences Scale
At Rx	Process	Satisfaction with Therapy
End-of-Study	Chart Review and Database Extraction	Review of Service Use and Diagnoses from VA Databases; Reports from Compensation Examinations; Disability Determination by VBA; Distance between Veterans' addresses and VA site

Justification for Schedule of Assessments: The initial 4-week assessment follow-up date was chosen because results of Motivational Interviewing interventions have been detectable this quickly in other studies (Burke, Arkowitz et al. 2003); the later, week 12 assessment will allow for detection of later-emerging effects of other VA treatments preferentially attended by Veterans who received the SBIRT intervention.

The end-of-study service use assessments will be conducted in the middle of year 4. Virtually all of the last cohort of study participants will have service use data for the three months after claims adjudication available at that time; the highly-publicized delays in the awarding of benefits generally are caused by delays prior to the Compensation evaluation.

Time to Complete Assessments: The baseline assessment will take approximately two and a quarter hours to complete. Approximately 45-60 minutes are allotted for the CAPS and Life Events Checklist; ten minutes for each of the baseline questionnaires, SCID substance abuse module, and service use calendar; and twenty minutes for each of the other baseline assessments.

#### 4. Demographics and Other Characteristics

a. Baseline Characteristics Questionnaire: A questionnaire to characterize study participants has been culled from the questionnaire used in a prior multi-site study (Morrissey, Calloway et al. 2002) and in our current Benefits Counseling study. It is included as Appendix 2. It covers the following domains: demographics, military history, psychiatric history, employment, and legal status. It will also include a six-item measure of social support and the 10 items from the Attitudes Toward Seeking Professional Psychological Help Scale-Short Form (Elhai et al., 2008). This widely-used scale consists of two factors, one reflecting openness to

seeking treatment for emotional problems and the other reflecting value of seeking treatment and need for it.

Social support is measured as the number of people from six categories that would loan clients \$100, provide them with a ride to an appointment or provide them with emotional support if they were suicidal (Lam and Rosenheck, 1999).

The Questionnaire also includes the VA four-question screen for a presumptive diagnosis of TBI. A presumptive diagnosis of TBI is made when the Veteran responds positively in each of four domains:

- i. History of Potential Head Injury (e.g. blast, vehicular accident, wound above shoulders)
- ii. Symptoms Immediately After Injury (e.g. being dazed, not remembering event)
- iii. Problems Afterwards (e.g. memory problems or lapses, light sensitivity)
- iv. Problems in the Past 7 Days (e.g. memory problems, balance problems, headaches)

b. Montreal Cognitive Impairment Test (MOCA): The holders of the MOCA copyright allow its use within VA for non-commercial purposes. It is sensitive to impairment in domains prominently impacted by TBI such as visuospatial/executive functioning, attention, abstraction and in fact contains several items from the Core Brief Neuropsychiatric Battery (TBI Clinical Reminder) used at VHA to screen for TBI. A score of <26 indicates substantial cognitive impairment (Nasreddine, Phillips et al. 2005).

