#### Hypotheses for Evaluative Component:

1. Veterans with substance use disorders randomized to No-Additional-Treatment will have worse PTSD over time compared to Veterans without substance use disorders and will attend fewer weeks of mental health and/or substance abuse treatment, after accounting for baseline differences between substance users and non-users.
2. Attendance at treatment will be predicted by Veterans' perceptions that obtaining and maintaining VA benefits depends on attending PTSD treatment. Attendance at treatment will be negatively associated with the perception that VA benefits are more likely to be denied if a Veteran receives substance abuse treatment.
3. Long-term attendance at treatment (before Compensation exam to post-award notification) will be significantly impacted by the occurrence of the Compensation examination and determination of award. The effect of attitudes about how disability benefits are awarded will be significantly moderated by these time-varying covariates.

[figure not shown]

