#### 5. Analyses of the Relationship Between Attitudes About Compensation examinations and Outcome

*(Evaluative Specific Aim 2: Attendance at treatment will be predicted by Veterans' perceptions that obtaining and maintaining VA benefits depends on attending PTSD treatment):*

We hypothesize and will test in HLM regression models whether attendance at substance abuse and/or mental health treatment (and other outcomes) are predicted by the following, after accounting for appropriate covariates:

a. Veterans' perception that obtaining and maintaining VA benefits depends on treatment. Veterans' perceptions concerning the linkage between their status and receiving benefits will be derived for the three scales of the Disability Beliefs Scale which reflect perceived linkage of benefits to: (i) engagement in VA mental health treatment, (ii) being symptomatic from PTSD, and (iii) being abstinent from drugs and/or alcohol. Other scales will be analyzed if the factor analysis of the Disability Beliefs scale reveals another factor structure.

b. Subscales indicating that (i) Validation, (ii) Self-Other Considerations and (iii) Financial concerns were Veterans' reasons for seeking Compensation, as rated on the Disability Application Appraisal Inventory (Sayer, Spoont et al. 2004). We hypothesize that Veterans who rate themselves higher in having applied seeking "Validation (of being ill)" will be more likely to attend treatment, and that Veterans with higher ratings in "Self-Other (e.g. someone else urges Veteran to seek award)" or who applied for financial gain would be less likely to attend treatment.

c. Interactions between Disability Application Appraisal and Disability Beliefs Scale subscale variables. Reasons for seeking benefits and beliefs about disability application appraisal may interact to make treatment attendance more or less likely.

Covariates in these analyses will include those reflecting three main domains that have been associated with treatment attendance (Koenen, Goodwin et al. 2003):

- Predisposing factors: demographic variables (age, gender)
- Enabling factors that facilitate access to treatment: study site, distance between home and medical center calculated using G.I.S. mapping
- Need for treatment: Substance Use, PTSD severity (CAPS total score) and depression severity (Beck Depression Inventory).

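### The models for Evaluative Hypothesis 2 adjust for no measure of general readiness to seek treatment, although a help-seeking attitude scale is collected at baseline and named in no analysis

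*Combined protocol and SAP*

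**What the plan says.** Under G. Assessments, item 4 (Demographics and Other Characteristics), the baseline questionnaire includes "the 10 items from the Attitudes Toward Seeking Professional Psychological Help Scale-Short Form". The same item describes two factors: how open the respondent is to getting help with emotional problems, and how far he or she values treatment and feels a need for it. The Schedule of Assessments places the questionnaire at baseline, to characterize participants ("Baseline Questionnaire (including TBI screen) MOCA").

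Evaluative Hypothesis 2 reads: "Attendance at treatment will be predicted by Veterans' perceptions that obtaining and maintaining VA benefits depends on attending PTSD treatment". Its second half expects lower attendance among Veterans who think that substance abuse treatment harms a claim.

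J.5 tests this in hierarchical models, after adjustment for covariates described only as appropriate. It then says: "Covariates in these analyses will include those reflecting three main domains that have been associated with treatment attendance". The predisposing domain holds age and gender only. The enabling domain holds site and the mapped distance from home to the medical center. The need domain holds substance use, the CAPS total and the Beck depression score. The help-seeking scale is in none of them.

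**The concern.** A Veteran who is generally favourable to treatment may be more likely to attend. The same Veteran may also answer the treatment-related items of the Disability Beliefs Scale differently, for example those on whether regular mental health attendance or taking psychiatric medication affects the chance of an award. If so, the belief coefficient in J.5 carries some of the effect of general attitude.

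This matters because of the use planned for the result. The Background (Significance of Proposed Studies) treats beliefs about compensation as modifiable, and points to an agency programme that responded to beneficiaries' perceptions. That inference needs the belief about claims to be distinguished from a general disposition toward care. The plan collects a measure of that disposition but does not commit to using it.

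**Working it through.** **1. Is the scale used anywhere?** Each list of variables in sections J and K was compared with the scale.

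| Section | Variables named | Scale named? |
|---|---|---|
| J.3 Missing data | Unspecified correlates of missingness | No |
| J.4 Aim 1 | Baseline outcome, gender, education, employment, BDI, response to stress, TBI | No |
| J.5 Aim 2 | Age, gender; site, distance; substance use, CAPS, BDI | No |
| J.7 Award | Site, demographics, depression, CAPS, pre-examination behaviours | No |
| J.8 Exploratory | Includes legal status, social support and employment, from the same questionnaire | No |
| K.2 Trial model | Baseline variables that differ between arms and relate to outcome | No |
| K.3 to K.5 | CAPS as mediator; predictors and moderators; process measures | No |

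**2. Does another J.5 covariate stand in for it?** The need variables measure severity. The Background itself reports, from a cited study, that service use was not associated with more severe self-reported PTSD symptoms. Baseline level of the outcome is a stated covariate in J.4 but not in J.5. Even if prior attendance were added, it would be a partial proxy. In the plan's chart review at the Connecticut site (B.4.b), only 47% had any mental health treatment, and 3% any VA substance abuse treatment, in the three months before the evaluation. The treatment-interest item of the Motivation for Change scale (G.12.a) is also collected at baseline, but is analysed only as a process measure in K.5.

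**3. How large could the effect be?** The plan states no figure to reproduce. What follows is an illustration.

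- From the documents: N = 560 (J.1, participants who did not receive SBIRT); 640 = 480 + 160 if everyone is analysed.
- Assumed: r, the correlation of attitude with belief; b, the standardized effect of attitude on attendance; no true belief effect; two-sided α = .05; one attendance value per person.

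With attitude omitted, the expected belief-attendance correlation is ρ = r × b. The noncentrality is ρ√N / √(1 − ρ²), and the rejection rate is 1 − Φ(1.96 − ncp) + Φ(−1.96 − ncp).

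Example, r = b = .3: ρ = .09; ncp = .09 × 23.66 / .996 = 2.14; rejection rate = .571.

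| r = b | ρ | N = 560 | N = 640 |
|---|---|---|---|
| .1 | .01 | .056 | .057 |
| .2 | .04 | .157 | .173 |
| .3 | .09 | .571 | .628 |
| .4 | .16 | .970 | .984 |

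Unequal values at N = 560: .1 with .2 gives .076; .1 with .3 gives .109; .2 with .3 gives .296.

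If r is negative, the bias reverses. With r = −.3 and b = .3, ρ = −.09, which would offset a true positive belief effect of about that size.

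**4. What does adjustment cost and achieve?** The standard error of the belief coefficient is multiplied by 1/√(1 − r²): 1.005, 1.021, 1.048 and 1.091 for r = .1, .2, .3 and .4, before any gain from explained variance. The share of residual variance removed, beyond a model with belief alone, is b²(1 − r²)/(1 − r²b²). That is .0384/.9984 = 3.8% at .2 and .1344/.9744 = 13.8% at .4.

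Adjustment is incomplete if the scale is measured with error. At an assumed reliability of .8 and r = b = .4, each observed correlation with attitude is .4 × √.8 = .358. The partial belief-attendance correlation is (.16 − .128)/(1 − .128) = .037, and the rejection rate is about 14%: far below 97%, but above 5%.

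**The case against.** A reader might infer that the belief effect cannot be separated from general attitude, or that a policy conclusion from Hypothesis 2 would be wrong. The documents support neither. The scale is in the data, and J.5 is open-ended: it speaks of appropriate covariates and says what they will include, without closing the list. The gap is one of commitment. That still matters, because open wording commits to nothing, and a covariate chosen after the belief coefficient has been seen offers weak protection.

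The direction of confounding is not documented either. The Disability Beliefs Scale asks how a Veteran's circumstances alter the chance of an award, which is a view of how claims are decided and not of whether treatment is worthwhile. One treatment-related example is improvement with treatment, which a Veteran who values care might think lowers the chance of benefits. The association could be positive, zero or negative. This stands, and the point is worded accordingly.

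The strongest objection concerns the remedy. Beliefs and attitudes are both measured at baseline. If believing that benefits depend on treatment raises its perceived value, attitude lies on the path from belief to attendance, and adjustment removes part of the effect under test. This stands too. It rules out deciding Hypothesis 2 on the adjusted coefficient alone, but not reporting both.

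The illustration also assumes its correlations, starts near 5%, ignores the covariates already in J.5 and simplifies the planned model. It shows that the omission can matter, not how much it does. Finally, the treatment-interest item might be a more direct measure of readiness. It is equally absent from J.5, so this supports the gap.

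**Conclusion.** The point holds in a limited form. J.5 as specified contains no measure of general readiness to seek treatment, and a baseline scale that measures it has no named analytic role. General attitude is therefore an unaddressed potential confounder of the belief-attendance association.

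Under the stated assumptions, the chance of a spurious belief effect runs from about 6% (correlations of .1, negligible) through 16% and 57% to 97% (correlations of .4). Those correlations, their equality and their sign are assumptions. With a negative attitude-belief correlation, the omission could hide a true effect. The supportable statement is that a policy reading of an unadjusted belief effect could be mistaken, not that it would be. Evaluative Aim 2 is observational, and the randomized SBIRT comparison is not affected.

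**What to change.** In J.5, name the two baseline factor scores of the help-seeking scale as added covariates in the models of attendance on the Disability Beliefs and Disability Application Appraisal subscales. Report the belief coefficients with and without them.

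State the interpretation in advance:

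- A belief effect is read as specific to the claim only if it persists after adjustment.
- Attenuation is reported as compatible with either confounding or mediation, because beliefs and attitude are measured at the same visit.
- Adjustment reduces the bias but does not fully remove it if the scale has measurement error.

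The change takes a few lines in J.5 and needs no new data. It uses two degrees of freedom. For attitude-belief correlations of .1 to .4, it widens the standard error of the belief coefficient by about 0.5% to 9%, before any gain from explained variance. The remaining risk is over-adjustment, which the paired report makes visible.

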## 5. Assessments of Attitudes and Beliefs about Compensation

a. The Disability Application Appraisal Inventory's test-retest reliability, internal consistency, factor structure and validation against selected MMPI subscales were tested and the measure has good reliability and construct validity (Sayer, Spoont et al. 2004). The Inventory asks the Veteran to rate his/her reasons for seeking service connection. Factor analysis has yielded three subscales reflecting different reasons for seeking Compensation (Sayer, Spoont et al. 2004). The "validation" subscale involves seeking benefits to "show that there is a reason for my problems," "feel like justice has been served," and "feel less like I am to blame for my problems." The "Self-Other Acceptance Scale" largely reflects interpersonal issues such as "My family wants me to become service-connected for PTSD." The "Financial Benefits" subscale items reflect seeking compensation to obtain money.

b. It has been assumed that Veterans have attitudes that can be paraphrased as "A Veteran who attends mental health treatment is more likely to get service-connected benefits than one who does not," "A Veteran who reports using illegal drugs is less likely to get service-connected than one who denies using, and "A Veteran who works is less likely to get service-connected than one who does not." Existing rating scales do not fully capture the belief that a Veteran's receipt of Compensation benefits is influenced by whether the Veteran (a) attends treatment, (b) recovers from the disabling illness, or (c) is judged to have alcohol or drug-related problems.

The Disability Beliefs Scale (attached as Appendix 3) asks Veterans to indicate how much a Veteran would affect his or her chance of getting Compensation Benefits on a scale from "Much Less Likely to Get Benefits" to "Much More Likely to Get Benefits" if the Veteran was in any of the following categories (a) engaged in VA treatment, (b) symptomatic from PTSD, and (c) abstinent from drugs and/or alcohol. For example, the Veteran is asked to rate on an interval scale whether the following treatment-related situation would make it more or less likely a Veteran would be awarded Compensation Benefits: "The Veteran takes medication for a psychiatric condition," "The Veteran is attending mental health treatment regularly," and "The

Veteran's symptoms have gotten better with treatment." A confirmatory factor analysis will be conducted of the Disability Beliefs Scale to determine if the anticipated three factor structure emerges, and continuous subscale scores for each factor will be considered separately in the data analyses.

Items for the Disability Beliefs Scale were drawn from existing measures that rate related constructs. The items concerning the relationship between treatment and receipt of disability payments were adapted from items used in a completed study of supportive employment at VA (Rosenheck and Mares 2007). Items were also drawn from the "Negative Expectations" subscale of the Disability Application Appraisal Inventory (not the same scale that rates reasons for seeking disability payments).

6. Substance Use Calendar and Ethyl Glucoronide (ETG): The timeline follow-back Substance Use Calendar assesses substance use on a daily basis. The use of a calendar format prompts participants to remember key dates. It allows for collection of data points for participants who miss evaluation sessions and thus prevents missing data and problems associated with overlap of data points. Timeline follow-backs have been sensitive to change in research settings (Weiss, Greenfield et al. 1998) and can be valid in patients with concomitant psychiatric illness (Petrakis, Poling et al. 2005).

Ethyl Glucoronide is produced and equilibrates throughout nail beds, thus allowing measurement by any nail sample of sufficient weight. Approximately 10mg of nail is required for analysis, which can be obtained from 10mm (a quarter's width) of nail from each of ten digits. Nail-clippers soaked for 10 minutes in 70% rubbing alcohol are used for the actual clipping. Nail levels of ETG have correlated with self-reported number of drinks among college-aged women at .51 and men at .64, with the lower correlation among women possibly reflecting greater use of nail care products (Jones, Jones, et al., 2011).

M. Jones, J. Jones, D. Lewis, C. Plate, M. Fendrich, L. Berger, & D. Fuhrmann. (2011, June). Correlation of the alcohol biomarker ethyl glucuronide in fingernails and hair to reported alcohol consumed. Poster session at the annual conference for the Research Society on Alcoholism, Atlanta, GA.

Samples will be processed at the United States Drug Testing Laboratories (Illinois) with no identifying information other than the study number. After processing, samples will be destroyed following a standard storage period.

## 7. PTSD Assessments

a. The Life Events Checklist (Weathers, Keane et al. 2001) inquires about whether the Veteran has had exposure to each of 17 classes of traumatic events. Veterans will be asked to identify the trauma causing the most current distress. Military sexual trauma will be defined by having had a sexual experience during military service that was unwanted and involved force or threat of force.

b. Clinician Administered PTSD Scale (CAPS): The CAPS is an extensively validated (Forbes, Creamer et al. 2001; Monson, Gradus et al. 2008) clinical interview used to derive a rating of PTSD symptom severity and diagnosis. It consists of 17 ratings of the frequency and severity of PTSD symptoms listed in DSM-IV-TR. Cluster subscales can be derived for the PTSD symptom clusters of hyperarousal, avoidance/numbing, and re-experiencing.

The CAPS takes 45-60 minutes to administer and requires a data collector with clinical experience. The CAPS is widely considered to be the gold standard measure of PTSD severity, and agreement between the CAPS and self-report measures such as the PTSD Checklist–Military has been variable (Monson, Gradus et al. 2008). Only the CAPS is observer-rated. The CAPS is more specific for PTSD than the PTSD Checklist because unlike the Checklist, the CAPS only rates emotional numbing and hyperarousal symptoms if they are not

accounted for by another disorder.

8. Beck Depression Inventory II is the updated iteration of the older Beck Depression Inventory. Respondents rate 21 statements reflecting the previous two weeks. The Beck includes items reflecting DSM IV somatic symptoms of depression and more cognitive factors associated with depression, and is thus well-suited to depression measurement among people with a high prevalence of somatic symptoms related to substance use. It showed excellent receiver-operating characteristics in identifying depressed Veterans from a cohort of Veterans with TBI and frequent comorbid PTSD (Homaifar, Brenner et al. 2009). Depression has been strongly associated with function among people with PTSD (Hoge, McGurk et al. 2008).

9. The Response to Stressful Experiences Scale contains 22-items describing the respondent's characteristic methods for dealing with stressful experiences. Each item is rated on a 5-point scale indicating the extent to which the item describes a method used by the respondent. Variability among participants in the availability and use of methods to deal with stressful experiences has accounted for variance in severity of PTSD symptoms in military samples (Johnson, Polusny, Erbes et al., 2011).

11. Self-Reported Service Use: A timeline-follow-back method will be used to determine service use during the preceding 60 days. An important benefit of this approach over summary measures is that it minimizes problems associated with information being collected twice for the same service, such as detoxification counted as a medical hospitalization and as substance abuse treatment, and it minimizes problems associated with overlapping data points. The questions about service use will be drawn from the Treatment Services Review (McLellan, Alterman et al. 1992) and the Program and Client Cost-Substance Abuse Treatment (PACC-SAT). The Treatment Services Review includes inquiries about each of the 7 domains explored in the Addiction Severity Index. The PACC-SAT was adapted from the DATCAP and involves questions about different types of services received.

The Service Use calendar has been modified to address analyses that will be conducted in the proposed studies. Specifically, the data collector will code services by non-substance use providers by whether they addressed substance abuse. As shown in the chart review of OEF/OIF Veterans who sought Compensation at VA Connecticut, more OEF/OIF Veterans with PTSD claims received mental health services than specialty substance abuse services. However, VA service use data cannot be used to determine whether people with substance use problems are having those issues addressed if they attend mental health treatment. Therefore, the service use calendar we will be using for self-reported treatment attendance includes inquiries concerning whether substance abuse was addressed during other mental health treatment.

The service use calendar also had questions added to determine what non-VA treatment Veterans received. Data will also be coded by whether it reflects VA or non-VA treatment. Additional questions have been added to determine satisfaction with VA services. Veterans are asked how satisfied they are with the VA services they receive on a 6 point scale.

